## 1 INTRODUCTION

This document describes the statistical analyses and the different layouts for tables and listings to be produced for the protocol **LyMa101** titled *“Phase II study to evaluate the efficacy of upfront obinutuzumab in mantle cell lymphoma patients treated by DHAP followed by autologous transplantation plus obinutuzumab maintenance then MRD driven maintenance”*.

One interim analyse for the primary criterion is planned for this study.

The statistical analysis plan (SAP) provides a comprehensive and detailed description of the strategy, rationale, and statistical methods to be applied to assess the efficacy and safety of Obinutuzumab (GA101), in patients with previously untreated MCL treated by DHAP.

The purpose of the SAP is to ensure the credibility of the study findings by pre-specifying the statistical approaches for all data analysis before database lock.

The SAP is finalized and signed prior to the clinical database lock.

## 2 INVESTIGATIONAL PLAN

### 2.1 Rationale

Achievement and preservation of minimal residual disease (MRD) response is the strongest independent predictor of prognosis in MCL patients. By using MRD status as tool for treatment selection, treatment should be focused to achieve and maintain a maximum MRD response to improve outcome. (Pott Blood 2010, Abstract ASH 2014).

Because of the economic constraints of maintenance therapy, preemptive treatment using rituximab based on MRD relapse should be evaluated and might be effective at preventing clinical relapse. Indeed, it has been shown in 32 MCL patients that MRD-based preemptive rituximab therapy restored a PCR-negative state in 81% of cases, of whom 38% subsequently relapsed clinically at a median time of 3.9 years (Andersen JCO 2009, Geisler BJH 2012). Pre-emptive treatment may thus prevent relapse in at least some patients and may prove to be a more cost effective strategy. Use of pre-emptive treatment requires definition of molecular relapse, which is classically based on a progressive rise in MRD levels in three consecutive samples, which can be increasingly closely spaced.

[figure not shown]
The gold standard for monitoring MRD in MCL is real-time quantitative polymerase chain reaction (RQ-PCR) amplification of clonal immunoglobulin heavy chain (IgH) VDJ or IgH-BCL1 rearrangements, which are informative in 90% and 40% of patients respectively (Pott Blood 2006, Andersen JCO 2009). RQ-PCR strategies are sufficiently sensitive (minimum 0.01%) and specific for MRD quantification in around 85% of MCL patients. These strategies are, however, long, complex and associated with a significant grey zone of non-quantifiable positivity, Below the Quantitative Range (BQR). The quantifiable range (QR) should ideally be at least 0.01% (10E-4), but this is not achieved in 20-25% of samples (Cheminant et al. submitted). For these reasons, RQ-PCR is increasingly challenged by multicolor Flow cytometry (MFC) or droplet digital PCR (ddPCR).

Approximately 10% of MCL patients are not accessible to RQ-PCR MRD with acceptable sensitivity and QR. A proportion of these cases become accessible to MRD assessment by MFC (Cheminant, submitted) or by PCR quantification relative to patient specific plasmid calibrators (Gimenez et al. BJH 2012). The use of MRD results for patient stratification obviously requires maximal informativity. Therefore, the present project will also investigate complementary techniques, including MFC, ddPCR and/or plasmid calibrators.

During follow-up, the percentage of MRD positive samples was approximately 20-25% during the first 3 years, and less than 20% at later time points (Pott ASH 2014 abstract 147). Among patients with clinical relapses, it has been shown that clinical relapse is strongly associated with MRD positivity. In an analysis of the EU-MCL network, only 13% of MCL patients were peripheral blood (PB)-negative (Pott ASH 2014 abstract 147), whereas this will be the predominant source of material for MRD analysis in the proposed study, for ease of sampling, patient comfort and because informativity is comparable to bone marrow analysis, particularly at later time points.

To the present trial will determine what proportion of patients' clinical relapse is preceded by molecular relapse and with what delay. In the EU-MCL studies, the latency between the first positive MRD and the clinical relapse varies greatly between patients. The median latency for prediction by RQ-PCR when any increase to at least 2 positive triplicates was considered as MRD relapse was 22.5 months [range 1-48m] and 5 months [range 2-11m] when only results above 0.01% were considered positive, with no difference between RQ-PCR and MFC quantification (Cheminant et al. submitted).

## 2.2 Study Design

## 3 STUDY OBJECTIVES AND ENDPOINTS

### 3.1 Objectives

#### 3.1.1 Primary objective

The primary objective of the study is to evaluate the efficacy of upfront Obinutuzumab (GA101) at the molecular level (MRD) in bone marrow after induction, after the 4 cycles or at premature discontinuation, in patients with previously untreated MCL treated by DHAP..

#### 3.1.2 Secondary objectives

The secondary objectives of the study are:

- To evaluate the efficacy of the obinutuzumab in patients with MCL treated by DHAP before ASCT, after ASCT and every 6 months in terms of clinical response (Cheson 99) and MRD plus in terms of FDG-PET before and after ASCT
- To evaluate PFS, Overall survival at study end
- To evaluate the incidence of stem cell collection failure after obinutuzumab-DHAP = GA-DHAP
- To evaluate MRD negativity after 3 years of maintenance and maintenance “on-demand”
- To evaluate PET results after 3 years of maintenance
- Duration of MRD negativity
- To evaluate tolerability of obinutuzumab at induction and then “on-demand”

#### 3.1.3 Exploratory objectives

The exploratory objectives of the study is:

- To determine baseline prognostic factors on PFS and OS

### 3.2 Evaluation endpoints

#### 3.2.1 Primary efficacy endpoint

The primary endpoint is the Molecular residual disease (MRD) negativity after induction. Assessment of MRD will be based on molecular level in BM according to EU MCL network guidelines. Patient without MRD assessment (due to whatever reason) will be considered as MRD positive. This endpoint will be analyzed on efficacy set (ES) and also on modified efficacy set (mES) as sensitivity analysis.

### 3.2.2 Secondary efficacy endpoints

The following secondary efficacy endpoints will be analyzed using appropriate statistical methods.

#### 3.2.2.1 Secondary efficacy endpoint 1

##### Response according to Cheson 99 and overall response rate after 3 years of maintenance

Response after 3 years of maintenance will be evaluated. Assessment of response will be based on the International Workshop to Standardize Response criteria for NHL (Criteria for evaluation of response in Non-Hodgkin's lymphoma (Cheson, 1999)). Patient without response assessment (due to whatever reason) will be considered as non-responder. Overall (CR/PR) response rate will be also presented.

An additional analysis will be performed considering as non-responders all patients who relapsed or died during treatment phase even if they were prematurely treatment discontinued as responder during treatment phase.

This endpoint will be analyzed on efficacy set (ES) and on safety set (SS).

#### 3.2.2.2 Secondary efficacy endpoint 2

##### PET result after 3 years of maintenance

PET result after 3 years of maintenance will be evaluated. Assessment of PET will be based on Lugano 2014 criteria (according to Cheson & Al. J. Clinic Oncol 2015). See Appendix C (Reponse criteria for lymphoma – Lugano classification).

This endpoint will be analyzed on efficacy set (ES) and on safety set (SS).

#### 3.2.2.3 Secondary efficacy endpoint 3

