15.1.2 Secondary endpoints

15.1.2.1 Efficacy endpoints

Response according to Cheson 99 and overall response rate after 3 years of maintenance

Response after 3 years of maintenance will be evaluated. Assessment of response will be based on the International Workshop to Standardize Response criteria for NHL (Criteria for evaluation of response in Non-Hodgkin's lymphoma (Cheson, 1999) See Appendix 8). Patient without response assessment (due to whatever reason) will be considered as non-responder. Overall (CR/PR) response rate will be also presented.

An additional analysis will be performed considering as non-responders all patients who relapsed or died during treatment phase even if they were prematurely treatment discontinued as responder during treatment phase.

This endpoint will be analyzed on efficacy set (ES) and on safety set (SS).

PET result after 3 years of maintenance

PET result after 3 years of maintenance will be evaluated. Assessment of PET will be based on Lugano 2014 criteria (according to Cheson & Al. J. Clinic Oncol 2015). See Appendix 9 (Reponse criteria for lymphoma – Lugano classification).

This endpoint will be analyzed on efficacy set (ES) and on safety set (SS).

MRD after 3 years of maintenance and after maintenance “on demand”

Molecular residual disease (MRD) after 3 years of maintenance and after maintenance “on demand” will be evaluated. Assessment of MRD will be based on molecular level in BM according to EU MCL network guidelines. Patient without MRD assessment (due to whatever reason) will be considered as MRD positive.

This endpoint will be analyzed on efficacy set (ES).

PFS

PFS is defined as the time from inclusion into the study to the first observation of documented disease progression or death due to any cause. If a subject has not progressed or died, PFS will be censored at the time of last visit with adequate assessment.

This endpoint will be analyzed on efficacy set (ES) and on safety set (SS).

OS

Overall survival will be measured from the date of inclusion to the date of death from any cause. Alive patients will be censored at their last contact date.

This endpoint will be analyzed on efficacy set (ES) and on safety set (SS).

Stem cell collection failure

Stem cell collection failure will be evaluated after induction.

This endpoint will be analyzed on efficacy set (ES) and on safety set (SS).

Duration of MRD negativity

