15.2 Sample size calculation and tested hypothesis

Hypothesis:

We expect to have an increase of 15% of the MRD negativity in bone marrow (BM) rate for patients treated with GA-DHAP.

Based on the interim results of LYMA presented at ASH 2014, the MRD negativity rate were 65% (Legouill, ASH 2014). Nevertheless, in the LYMA study, the MRD has been assessed after 4 cycles of DHAP only for patient that completed the 4 cycles. Therefore this rate does not take into account the rate of patients who progressed on treatment or took R-CHOP because of insufficient response. If we take into account these patients considering them as non responder patients and based on the LYSA/LYSARC experience, then the MRD negativity rate of all patients in the LYMA may be around 55%. Considering that these patients will also be included in the LyMa101 we have to take into account a rate of 55% of MRD negativity instead of 65% in the sample size calculation.

The hypotheses are as follows:

- Experimental treatment will be considered ineffective if the MRD negativity in BM after the 4 cycles or at treatment discontinuation (at a molecular level) proportion is $\leq 55\%$ (P_0)
- Experimental treatment will be considered effective if the MRD negativity in BM after the 4 cycles or at treatment discontinuation (at a molecular level) proportion $\geq 70\%$ (P_1)
- α risk of 0.05 and β of 0.20
- one-sided test

Patients will be considered as MRD positive if the patient has no MRD assessment due to whatever the reason.

Sample Size:

A total of 70 evaluable patients will be required for this study. Assuming that some included patients will not receive the treatment or will not be informative for MRD in bone marrow and/or blood at baseline, enrollement will be done until 70 patients are evaluable. For this purpose, about 83 patients should be enrolling (15% drop-out).

Sample size calculation was performed using an exact single-stage phase II design with East 5.4 (A'Hern RP. Sample size tables for exact single-stage phase II designs. Stat Med. 2001. 20(6):859-66).

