##### MRD after 3 years of maintenance and after maintenance “on demand”

Molecular residual disease (MRD) after 3 years of maintenance and after maintenance “on demand” will be evaluated. Assessment of MRD will be based on molecular level in BM according to EU MCL network guidelines. Patient without MRD assessment (due to whatever reason) will be considered as MRD positive.

This endpoint will be analyzed on efficacy set (ES).

#### 3.2.2.4 Secondary efficacy endpoint 4

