## 4 STATISTICAL CONSIDERATIONS

### 4.1 Sample size calculation

#### Hypothesis:

We expect to have an increase of 15% of the MRD negativity in bone marrow (BM) rate for patients treated with GA-DHAP.

Based on the interim results of LYMA presented at ASH 2014, the MRD negativity rate were 65% (Legouill, ASH 2014). Nevertheless, in the LYMA study, the MRD has been assessed after 4 cycles of DHAP only for patient that completed the 4 cycles. Therefore this rate does not take into account the rate of patients who progressed on treatment or took R-CHOP because of insufficient response. If we take into account these patients considering them as non responder patients and based on the LYSA/LYSARC experience, then the MRD negativity rate of all patients in the LYMA may be around 55%. Considering that these patients will also be included in the LyMa101 we have to take into account a rate of 55% of MRD negativity instead of 65% in the sample size calculation.

The hypotheses are as follows:

- Experimental treatment will be considered ineffective if the MRD negativity in BM after the 4 cycles or at treatment discontinuation (at a molecular level) proportion is  $\leq 55\%$  ( $P_0$ )
- Experimental treatment will be considered effective if the MRD negativity in BM after the 4 cycles or at treatment discontinuation (at a molecular level) proportion  $\geq 70\%$  ( $P_1$ )
- $\alpha$  risk of 0.05 and  $\beta$  of 0.20
- one-sided test

Patients will be considered as MRD positive if the patient has no MRD assessment due to whatever the reason.

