## 4.5 General statistical approach

### 4.5.1 Statistical analysis

Continuous data will be summarized in tables displaying number of observations, mean, standard deviation, median, range; quartiles will also be presented when considered relevant.

Categorical data will be expressed as frequencies and percentages (of non-missing data).

Response rates (according to Cheson 1999 or MRD) will be expressed with 90% confidence limits (to be consistent with one sided 5% level of significance) according to Pearson-Clopper method. The number and percent of patients falling into each category of response will be provided.

Time to event will be performed using Kaplan-Meier method. Survival probabilities, median survival and quartiles will be estimated with their 95% CI. Survival curves will be provided. A dedicated analysis on survival (PFS/OS) will be performed in order to determine baseline prognostic factors. The implemented method will take into account the specificities of on-demand treatment during the second maintenance period.

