## 5.7.5 PET results

**Table 5.7-7 PET scan result – Efficacy Set**

	After Induction N=XX	After ASCT N=XX	After 3 years of maintenance N=XX	End of Treatment N=XX
PET scan				
No	XX (XX.X%)	XX (XX.X%)	XX (XX.X%)	XX (XX.X%)
Yes	XX (XX.X%)	XX (XX.X%)	XX (XX.X%)	XX (XX.X%)
If done, hypermetabolic lesion				
No	XX (XX.X%)	XX (XX.X%)	XX (XX.X%)	XX (XX.X%)
Yes	XX (XX.X%)	XX (XX.X%)	XX (XX.X%)	XX (XX.X%)
If yes, SUV Max tumoral				
N	XX	XX	XX	XX
Missing	XX	XX	XX	XX
Mean (SD)	XX.X (XX.XX)	XX.X (XX.XX)	XX.X (XX.XX)	XX.X (XX.XX)
Median	XX.X	XX.X	XX.X	XX.X
Q1 ; Q3	XX ; XX	XX ; XX	XX ; XX	XX ; XX
Min ; Max	XX ; XX	XX ; XX	XX ; XX	XX ; XX
If yes, localisation				
XXX	XX (XX.X%)	XX (XX.X%)	XX (XX.X%)	XX (XX.X%)
XXX	XX (XX.X%)	XX (XX.X%)	XX (XX.X%)	XX (XX.X%)

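### Year-3 PET is declared on the full Efficacy and Safety Sets, but with no rule for an absent scan its percentage is taken over scanned patients only

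*SAP*

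**What the plan says.** Three efficacy endpoints are read after 3 years of maintenance, in consecutive subsections of SAP 3.2.2.

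- Cheson response (3.2.2.1, ES and SS): "Patient without response assessment (due to whatever reason) will be considered as non-responder".
- PET (3.2.2.2, ES and SS): "PET result after 3 years of maintenance will be evaluated. Assessment of PET will be based on Lugano 2014 criteria". The definition then names the analysis sets and stops. Protocol 15.1.2.1 is the same: "PET result after 3 years of maintenance will be evaluated", with no rule for an absent scan.
- MRD (3.2.2.3, ES): "Patient without MRD assessment (due to whatever reason) will be considered as MRD positive".

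Two general rules cover whatever an endpoint leaves open. SAP 4.5.1 states: "Categorical data will be expressed as frequencies and percentages (of non-missing data". SAP 4.6 rules out imputation.

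The PET tables in SAP 5.7.5 (5.7-7 for the ES, and the table numbered 5.7-2 for the SS) first count scans done and not done, then give a No/Yes row headed "If done, hypermetabolic lesion". They carry no Lugano category, no rate row and no footnote on missing scans.

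Protocol 9.8 and Appendix 3 place the maintenance PET only at the end of the first 3 years. Protocol 9.9, which covers end of treatment and premature discontinuation, names CT but not PET, and the PET cell for that visit in Appendix 3 is empty.

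**The concern.** The endpoint is declared on whole analysis sets, yet the rules that apply to it remove everyone without a year-3 scan from the percentage. That removal is related to outcome. A patient who progresses, dies, cannot be transplanted after failed stem cell collection, or stops for toxicity will generally not have a PET at the end of 3 years of maintenance.

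The reported figure will stand beside two other year-3 results in which the same patients count as failures. A reader comparing the three would see PET look better partly because its denominator is smaller. Nothing in either document gives a reason for treating PET differently.

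**Working it through.** **1. Which rule governs an absent year-3 assessment**

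| Year-3 endpoint | Declared on | Rule for no assessment | Denominator that follows |
|---|---|---|---|
| Cheson response | ES, SS | non-responder | full set |
| PET | ES, SS | none; SAP 4.5.1 and 4.6 apply | scanned patients |
| MRD | ES | MRD positive | full set |

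The year-3 MRD table (5.7.6-1) also lacks a footnote, but the text of 3.2.2.3 governs it. No text governs PET. The primary-endpoint table (5.7.1.1-1) shows that the SAP does use such a footnote elsewhere.

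**2. Inputs**

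- N = 70, the planned evaluable number (Protocol 15.2, SAP 4.1). The plan states no figure for PET, so this is the only design figure used. It reproduces: with null 55%, alternative 70% and success at 46 or more of 70, the exact binomial one-sided alpha is 0.0452 and power is 0.820. Enrolment is 70/(1 − 0.15) = 82.4, rounded up to 83.
- m, the share of the set without a year-3 PET: not in the documents. Assumed 10% to 40%.
- p, the share without a hypermetabolic lesion among those scanned: not in the documents. Assumed 90%, with 80% to 95% as a range.

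**3. Formulas**

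With x lesion-free patients, the SAP's rules give x/[N(1 − m)]. The convention of the neighbouring endpoints gives x/N. The ratio is 1/(1 − m): 1.11, 1.25, 1.43 and 1.67 at m = 10%, 20%, 30% and 40%. The gap is p − p(1 − m) = p × m.

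**4. Results for N = 70 and p of about 90%, in whole patients**

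| m | Unscanned | Scanned only (90% CI) | Full set, absent = failure (90% CI) | Gap (points) | Full set, absent = lesion-free |
|---|---|---|---|---|---|
| 10% | 7 | 57/63 = 90.5% (82.1–95.8) | 57/70 = 81.4% (72.1–88.7) | 9.0 | 64/70 = 91.4% |
| 20% | 14 | 50/56 = 89.3% (79.9–95.2) | 50/70 = 71.4% (61.2–80.2) | 17.9 | 64/70 = 91.4% |
| 30% | 21 | 44/49 = 89.8% (79.7–95.9) | 44/70 = 62.9% (52.4–72.5) | 26.9 | 65/70 = 92.9% |
| 40% | 28 | 38/42 = 90.5% (79.5–96.7) | 38/70 = 54.3% (43.8–64.5) | 36.2 | 66/70 = 94.3% |

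Intervals are Clopper-Pearson. With p from 80% to 95% the gap is 8–10 points at m = 10%, 16–19 at 20%, 24–29 at 30% and 32–38 at 40%. The SS will be somewhat larger than the ES. At the enrolment figure of 83, an upper limit for it, the gaps with p of about 90% are 8.7, 18.3, 27.0 and 35.8 points, so set size hardly matters.

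The last column gives the opposite extreme. The scanned-only figure lies close to what would hold if nearly every unscanned patient were lesion-free.

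**The case against.** **The tables define no PET-negativity rate.** They describe scans, lesions, SUVmax and sites, and their first row prints how many patients were not scanned. This stands in part. A reader could rebuild the full-set figure if the column N is the full set, but the shells do not define N, and disclosing the number unscanned does not score those patients. The shells also contain no row in the Lugano terms that 3.2.2.2 requires.

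**Metabolic categories already appear in the SAP.** The year-3 response tables in SAP 5.7.4 list complete, partial, no and progressive metabolic outcomes with a not-evaluated row. But they are titled Cheson 99 and serve endpoint 1, so they supply no rule for endpoint 2.

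**A scan at early discontinuation is not excluded.** Protocol 9.9 has a general item for repeating baseline response procedures, and PET is a baseline procedure. That may permit a scan but does not schedule one, and a PET at discontinuation is not a year-3 result. In addition, patients without informative baseline MRD leave treatment after the first 3 years (Protocol 9.10), so their year-3 scan may be recorded as end of treatment. This is a good reason not to delete that column.

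**Counting absent scans as failures is a convention, not the truth.** Some patients who stopped in remission may be PET-negative. This stands: the inflation is relative to the plan's own convention at this time point, not to a known true rate.

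Two stronger readings are tempting. A reader might infer that the percentage covers survivors only. The condition is being scanned, which also leaves out living patients who progressed, stopped, withdrew or missed the scan. A reader might also take the plan's correction from 65% to 55% as an attrition rate (1 − 55/65 = 15.4%). It is an approximate MRD adjustment from a rituximab-based trial, for patients who progressed or switched to R-CHOP. It does not measure departure before year 3, and in this trial stable disease still proceeds to transplant (Protocol 10.2.2). The documents therefore support no single figure for the overstatement.

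**Conclusion.** The point holds. As written, the SAP puts the year-3 PET percentage on scanned patients although the endpoint belongs to the full ES and SS, and the omission depends on outcome. Relative to the absent-equals-failure convention used for year-3 Cheson response and MRD, the inflation factor is exactly 1/(1 − m). Its size in points rests entirely on assumed values of m and p.

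The consequence is limited. This is a descriptive secondary endpoint with no test or threshold, and the 46-of-70 decision rule does not depend on it. It should still be corrected before database lock, because three year-3 results on different denominators will otherwise be read side by side.

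**What to change.** 1. In SAP 3.2.2.2 add: *Patients of the analysis set without a PET after 3 years of maintenance, whatever the reason, are counted as not in complete metabolic response; this overrides 4.5.1 and 4.6 for this endpoint.*
2. In both PET tables of SAP 5.7.5 add, for year 3, the Lugano metabolic categories and a complete metabolic response rate over the full ES or SS, with 90% Clopper-Pearson limits as in 4.5.1. Scoring needs these categories, because the present rows record only lesion No/Yes.
3. Keep the scanned-only percentage as a labelled supplement, with the number scanned and the reasons for no scan (progression, death, discontinuation, not done).
4. Keep the End of Treatment PET column, labelled as scans not scheduled by Appendix 3. Check that a year-3 scan recorded at the end-of-treatment visit of a patient without informative MRD is counted under year 3.

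The cost is one sentence and a few table rows, with no new visits or scans. The downside is that the reported PET rate becomes less favourable and some patients who stopped in remission are counted as failures. The supplementary row lets a reader judge how much that matters.
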